Two hundred twenty-four (112 Distressed Violent and 112 Distressed NonViolent) couples will be enrolled in the study. We will screening 1200 couples in order to obtain the number to be enrolled in the study.

7) Recruitment Methods

Recruitment will be conducted using strategies discussed in Holtzworth-Munroe et al. (1992) for recruiting distressed violent couples (e.g., advertising for distressed couples) and will be conducted at the couple level. The Albuquerque, NM metropolitan area has a population of approximately 900,000, which is sufficiently large for the recruitment of a specialized sample. No recruitment will take place in domestic violence shelters, court mandated treatment settings, or through court referrals. Evidence suggests that individuals recruited from these locations are more likely to be generally violent (violence outside the family), have severe personality disturbances (antisocial personality

disorder), and have involvement in other criminal activity (1992). Participants will be recruited via advertisements placed throughout the Albuquerque Metro area, local newspapers, online forums, list serves, radio spots and television interviews. In addition, advertisements will be placed on ResearchMatch.org. Because of concerns about an invasion of privacy and the sensitivity of the data collected in this study, flyers will refer to generic aspects of relationship dissatisfaction and alcohol consumption.

In advertising for couples who drink alcohol weekly we have determined that this statement on the recruitment flyer or ad is selecting, almost exclusively, for individuals who have an alcohol use disorder or who are alcohol dependent, and therefore ineligible for our study. We are requesting permission to also place advertisements that do not include the “drink alcohol weekly” aspect of the inclusion criteria in the ad. The ad will continue to indicate that participants may consume alcohol during one or both experimental session, and we will continue screen for alcohol use consistent with our inclusion criteria (AUDIT score no greater than 19 and two binge episodes in previous month). (Please see the attached versions of the advertisement for the recruitment script and for how posted flyers will appear.)

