Potential participants may endorse drinking levels making them ineligible for the study (AUDIT greater than 19). Such individuals will be given feedback regarding the drinking measures, and given referral information by the study staff or [name]. Following NIH guidelines, this referral will be an active referral. The staff member will present such individuals with a menu of options, provide a suggestion about a treatment option that is a good match, and will offer to call the facility and make an appointment for the individual.

8) Study Timelines

Participation in this study by participants will take a total of eight (8) hours over three sessions. Session one, the *Stimuli Acquisition Session*, will take two (2) hours and both partners of each couple will participate. Sessions two and three, the *Emotion-Regulation Sessions*, will be either a placebo or alcohol administration session. Participation in the placebo session will take one (1) hour. Participation in the alcohol administration session will take five (5) hours. The emotion-regulation and response inhibition tasks lasts approximately 30 minutes in each of the experimental sessions. The additional time in each session accounts for study set-up (attaching electrodes, etc.) and detoxification from alcohol in the alcohol-administration experimental session.

We anticipate enrolling study participants for two years and primary data analysis will be complete six months after the last participant is enrolled.

9) Study Endpoints

The study will be terminated if it is determined that the study procedures have resulted in a violent argument where physical aggression, including throwing or hitting the partner with an object that could inflict pain or injury, has occurred between three or more couples.

10) Research Setting

The UNM Clinical and Translational Science Center houses [name] laboratory where the study will be conducted.

11) Study Methods

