Note that participants who are deemed ineligible for participation will be given a list of area resources for assistance with relationship distress and/or partner violence, including procedures for filing for an order of protection. Participants will be required to bring a current state issued identification card (e.g. driver's license) to verify that they are at least 21 years of age. Furthermore, DV and DNV partners selected for participation in the *Emotion-Regulation Sessions* will receive instructions not to drive to their individual study sessions during their initial phone screen because of the possibility of receiving alcohol. This will be reiterated at the initial *Stimuli-Acquisition Session*. Participants will be required to have someone other than their partner (e.g., friend or family member) pick them up from the individual sessions. Alternatively,

participants will be provided with taxi vouchers if they need transportation back to their home address following detoxification. Female participants will provide a urine sample for a pregnancy test before the alcohol administration condition and the placebo condition (to maintain blindness of participants to condition). The female partner will be excluded from the study if the test reveals she is pregnant.

Stimuli Acquisition Session: Self-report instruments of relationship functioning, alcohol consumption, impulsivity, executive functioning and state/trait anger will be administered to both partners of each couple type (DV, DNV) separately. (Data from partners not selected for the emotion-regulation task will be preserved for future dyadic data analyses.) Partner stimuli for use in the emotion-regulation task will be acquired via the researcher facilitated Couple's Problem Inventory (CPI). The CPI ensures couples discuss an emotionally salient area of disagreement so that the laboratory discussion will mirror discussions at home to the degree possible in a laboratory setting. It is important to note the purpose of the researcher facilitated CPI interview is to ensure the couple discusses an emotionally salient area of disagreement so that the laboratory discussion will mirror such discussions at home to the degree possible in a laboratory setting. Any emotional carry-over from the self-report measures will only facilitate this process. Partners will be directed to discuss the topic and attempt to reach a resolution.

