Specifically: Alcohol dose (g) = $((10 * \text{BAC} * \text{TBW})/0.8) + (10 * \text{MR} * (\text{DDP} + \text{TPB})) * (\text{TBW}/0.8)$. Participants will be asked to drink the beverage within 10 minutes to ensure that they remain on the ascending limb or reach peak BAC during the 25-minute experimental task. After completion of the experimental task, participants will continue to be breathalyzed every 15 minutes and when their BAC is less than 30 mg/dl (.03%), they will be excused.

Placebo Condition Protocol - Procedures will be identical to the alcohol condition, except participants will consume a volume of juice equivalent to that consumed in the alcohol condition with a small amount (~3 ml) of alcohol floated on top of the juice and misted with vodka to produce the taste and smell of alcohol. Participants will then complete the emotion-regulation task while biopotential data are collected.

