3. On a yearly basis, the PIs will file a report to HRRC that contains all adverse events that occurred in the prior year. The study will be terminated should it be determined that study procedures resulted in violent arguments in three or more couples.
4. All female participants will be required to take a urine-based pregnancy test on any day in which they will participate in the experimental conditions (placebo and alcohol). If a participant tests positive for pregnancy, she will not be allowed to continue with the study and will be paid at a prorated rate.
5. The PI and collaborators for the study will always be present or on call while participants are undergoing administration of alcohol.
6. The study will involve administering alcohol to participants, and will be done in accordance with NIAAA guidelines for administering alcohol in human studies (www.niaaa.nih.gov/Resources/ResearchResources/job22.htm). All participants will be 21 years of age or older. Before administration participants will be notified of how much alcohol they will receive in terms of standard drinks and peak blood alcohol range in plain English, and will also be informed about the length of time required to participate in the study and for their blood alcohol levels to return to safe levels (<.03g%). Participants will be instructed not to drive to appointments. Once the experiment is completed, participants will be directed to a private assessment room that is near a bathroom that can be monitored easily by research associates. Participants will also be provided with snacks and water after participating. Before participants will be allowed to leave the CTSC laboratory, two consecutive breath alcohol concentration readings that are .03g% or below will be required. Finally, participants will be compensated with a gift card payment of \$40 after the placebo session and \$100 after the alcohol session. The alcohol session payments include the time during which the participant is decreasing to .03g%.
7. Referral to treatment: We are excluding participants who meet DSM-IV criteria for alcohol dependence based on an initial phone screen. If participants meet diagnostic criteria for alcohol dependence at the laboratory visit, however, they will be provided with an active referral consisting of a research staff contacting local treatment facilities if the participant so chooses. The study does not have a follow-up phase so we will not monitor increases in alcohol use over time.

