N/A. Research is experimental and will be conducted in [name] laboratory housed in the CTSC.

22) **Sharing of Results with Subjects/Incidental Findings**

At this time, our behavioral study procedures do not lend themselves to the discovery of incidental findings. At the conclusion of the study procedures, all participants will be informed of the study hypotheses.

23) **Resources Available**

Drs. [name] and [name], as well as their collaborators have conducted studies that use overlapping methodology with the current study, including the measurement of psychophysiological responses (i.e. pupillometry, skin conductance and heart rate variability), and measurement of acute alcohol effects on executive control. First, [name] has published couples research examining the effects of intraindividual responses to relationship distress and their effects on depressive symptoms. She has also published behavioral methods for improving adaptive behavioral displays of couples in therapy sessions that improve generalization and utilization of new skills outside of therapy. In addition, [name] has published studies in which skin conductance response, and heart rate variability were the dependent variables. [name] has conducted both oral and

intravenous route alcohol administration studies to examine how individual differences in alcohol induced impairment relates to subjective measures of sensitivity to the effects of alcohol (R21-AA020304). [name] has published pupillometry data during task performance, and has shown differences in pupil diameter in response to individually salient stimuli. As seen in Figure 2, pupil diameter was increased, an indication of increased arousal, during the recognition of the salient stimuli. Finally, [name] has published research using nearly all common techniques associated with human autonomic system functioning, and has applied them to assessments of cognitive and affective control.

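### The pre-drink notice of alcohol amount is not reconciled with participant blinding, and session length and pay can reveal the beverage in the second emotion-regulation session

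*Combined protocol and SAP*

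**What the plan says.** Section 15, item 6, on alcohol safety: "Before administration participants will be notified of how much alcohol they will receive in terms of standard drinks and peak blood alcohol range". The same sentence adds "the length of time required to participate in the study" and the time needed for blood alcohol to return to a safe level.

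Section 11 (Study Methods) points the other way. Pregnancy tests are done at both beverage sessions "to maintain blindness of participants to condition". For the placebo, "Procedures will be identical to the alcohol condition, except participants will consume a volume of juice equivalent" to the alcohol volume, with a "small amount (~3 ml) of alcohol floated on top of the juice and misted with vodka".

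Section 8 (Study Timelines): "Participation in the placebo session will take one (1) hour. Participation in the alcohol administration session will take five (5) hours". It numbers the stimuli acquisition visit as session one and the two emotion-regulation visits as sessions two and three. Pay also depends on condition: 100 dollars for alcohol against 20 dollars for placebo in section 11, or 40 dollars for placebo in section 15, item 6. The advertisement described in section 7 says that "participants may consume alcohol during one or both experimental session".

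Beverage order is counter-balanced. The ANOVAs in the Data Analysis Plan (section 14) contain beverage, stimulus, regulation condition (Aim 2 only) and partner type. Age is the only conditional covariate, and there is no order term.

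**The concern.** The placebo session exists so that the effect of alcohol can be separated from the effect of expecting alcohol. That fails to the extent that participants know their beverage before or during the task. A truthful statement of amount and peak concentration just before each drink would tell them. Even without such a statement, a participant sent home after about an hour, or kept for about five, can work out what the first drink was and so form a view about the second.

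At stake is the reading of Hypothesis 1a. Section 3 words it as comparable alcohol-related increases in the two partner types, but section 14 tests it as the beverage main effect on arousal. Arousal from believing that one has drunk alcohol adds directly to that main effect.

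**Working it through.** **The plan's own figures.** Section 8 gives 2 + 1 + 5 = 8 hours, which matches its stated total, so the 1-hour and 5-hour sessions are intended. Section 11 pay is 80 + 100 + 20 = 200 dollars per couple, as stated there. With the 40-dollar placebo payment of section 15 the sum is 220. Pay differs by condition on either figure. The documents give no alpha, power, effect size or SD behind 112 per group, so there is no power figure to reproduce.

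**What the notice could mean.**
- Truthful and given before each drink: it reveals the condition in both sessions.
- One study-level disclosure: the first emotion-regulation session stays blind.
- Active-dose wording repeated before placebo: blinding holds, but the statement is untrue, and no such deception is described.

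The protocol does not say which applies.

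**The length and pay cue.** It acts after the task of the first emotion-regulation session (document session two), so it can affect only the second (document session three). Under the advertised wording, someone who recognises a first placebo can expect alcohol next, while someone who had alcohol first cannot be sure. If participants know there is one session of each, both orders can infer.

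**Effect on Hypothesis 1a.** Let D be a person's alcohol-minus-placebo difference, β the beverage effect, π the session effect (second minus first) and d an expectancy shift in the placebo-first order only.
- Placebo-first: mean D = β + π + d
- Alcohol-first: mean D = β − π
- Pooled with equal orders: β + d/2

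As an illustration, d = 0.20 SD gives a shift of 0.20/2 = 0.10 SD. The orders differ by 2π + d, so a table by order cannot separate expectancy from practice or habituation.

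**Other hypotheses.** H1c (partner type × beverage × stimulus) is affected only if expectancy differs by partner type and stimulus; H2d needs a difference by regulation condition as well. H2a and H2c are tested within placebo and H2b within alcohol, so none of these is an alcohol-placebo contrast. H1b collapses across beverage.

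**What an order term does.** Assume π = 0.10, 0.25 or 0.50 in SDs of D.
- With 50:50 order, omitting the term inflates the SE by √(1 + π²) = 1.005, 1.031 or 1.118. Power for an assumed partner-type-by-beverage contrast of 0.375 SD (112 per group, two-sided 0.05) is 0.801 with the term and 0.797, 0.777 or 0.709 without it.
- If order were 60:40 in DV and 40:60 in DNV, the bias in that contrast without the term would be 0.4π = 0.04, 0.10 or 0.20 SD.
- With the term and balanced orders, the beverage estimate is still β + d/2.

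**Comparison restricted to the first emotion-regulation session.** In SDs of a person's session mean, with 112 per order: SE = √(2/112) = 0.134 and 95% half-width 1.96 × 0.134 = 0.262. The pooled within-person SE is √(2(1 − r)/224) = 0.079, 0.067 or 0.052 for an assumed between-session correlation r of 0.3, 0.5 or 0.7. The restricted SE is therefore √(2/(1 − r)) = 1.69, 2.00 or 2.58 times as large.

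**The case against.** The strongest reply is that item 6 of section 15 is a safety summary, and its reference to time required for the study suggests one disclosure covering the whole study. On that reading the notice leaves the first emotion-regulation session blind, and the consent form may say so. This stands: the conflict is unresolved, and unblinding is not shown. It does not answer the length and pay cue, which is present however item 6 is read.

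A second reply is that counter-balancing already protects the beverage contrast. For an additive session effect and equal orders that is right, so a reader who infers that the missing order term biases Hypothesis 1a goes too far. The omission costs precision, and it biases comparisons between partner types only if order is unbalanced between them. The documents do not say that order is balanced within DV and DNV.

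A third reply is that the damage is narrow and of unknown size. This also stands. As worded in section 3, Hypothesis 1a is not biased by an expectancy shift equal in both partner types.

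**Conclusion.** The point holds as a minor to moderate one. The protocol leaves open whether participants are told their beverage before drinking, and its own session lengths and payments give a route by which the second emotion-regulation session can be inferred. The main exposure is the beverage main effect, which moves by d/2 if a shift d is confined to the placebo-first order. This assumes equal numbers per order. The documents support no value or direction for d.

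A reader might infer that a fixed share of the data is unblinded. Counting second sessions gives 112/448 = 25% if only the placebo-first order can infer, or 224/448 = 50% if both can. These counts assume that every participant recognises the first beverage. They show how many sessions are open to inference and do not measure bias. Nor do the documents support the inference that all hypotheses are compromised.

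**What to change.** 1. Reconcile section 15, item 6 with the blinding and placebo text of section 11. Use the same truthful notice on alcohol amount, peak range, time and pay before both emotion-regulation sessions, worded so that it does not identify the condition and subject to review-board confirmation. The wording needs care, since staff know that each person has one session of each kind: it should describe what the study can involve and not predict that day's drink. The 20- versus 40-dollar placebo payment is a separate drafting correction.
2. Add session order (alcohol-first or placebo-first) as a between-subjects factor in the section 14 ANOVAs, including its interaction with beverage, which carries the session effect. Report the beverage effect by order. This handles session effects and any order imbalance between DV and DNV. It does not remove expectancy bias.
3. As a sensitivity analysis for Hypothesis 1a, report the between-person alcohol-versus-placebo comparison from the first emotion-regulation session only. State how order is allocated, since this comparison depends on it.
4. Optionally, ask one beverage-belief question after each task and report it descriptively beside the Subjective High Assessment Scale, which section 12 already lists but the analysis plan does not use.

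The cost is revised wording, one degree of freedom, one table and a less precise sensitivity estimate. None of this stops participants recognising intoxication or inferring the second session from the first. Making both sessions five hours would remove the length cue but would add 4 × 224 = 896 participant-hours, or 17,920 dollars at 20 dollars per hour, and is not proposed.
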